- 2. A molecular test that differentiates relapsing-remitting MS from progressive MS variants (AUROC of 0.91); and
- 3. A molecular test that predicts future rates of disability progression, concordance coefficient of 0.425 (p<0.001).

Because these results are derived from a single research center (NIAID/NDS), it is imperative to determine their performance in real clinical practice settings as a necessary step for their potential regulatory approval. Consequently, this application has 2 specific aims:

AIM 1. To independently validate afore-mentioned CSF-biomarker-based tests for their clinical value within the multicenter Spinal fluid Consortium for MS (SPINCOMS). In Aim 1, each of the 3 defined tests will be validated in 100 new SPINCOMS patients. To validate the prognostic test, 100 MS patients with CSF collected at least 3 years from the date of a follow-up study visit will be evaluated at follow-up examination with standardized clinical outcomes. CSF will be analyzed blinded using pre-defined statistical models.

AIM 2. To explore whether collected CSF-biomarkers point towards pathogenic heterogeneity that may predict patient-specific efficacy for different disease-modifying treatments (DMTs) or identify pathogenic mechanisms not targeted by current DMTs. In Aim 2, clustering analysis will assess pathogenic heterogeneity and explore potential predictors of response to therapy.

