1. STUDY DESIGN

Cross-sectional cohort studies (Figure 1.).

- For the MS diagnostic test, we will select 50 patients with definite MS (CIS/RIS excluded) and 50 controls, including 25 non-inflammatory neurological diseases (NIND) that mimic MS (such as patients with vascular-ischemic changes, complex migraines, leukodystrophies, etc.) and 25 other inflammatory neurological diseases (OIND) such as NMO, Susac's syndrome, sarcoidosis, CNS vasculitis.
- 2. For validating the RRMS versus progressive MS classifier, we will select CSF from 50 RRMS and 50 progressive MS patients (25 SPMS and 25 PPMS).

- 3. Cryopreserved CSF samples from these patients will be analyzed blindly using SOMAscan assay. Probability of MS diagnosis and progressive MS diagnosis will be calculated based on published models². Results will then be unblinded and analyzed for accuracy of diagnostic conclusion.
- 4. To evaluate the MS severity score, we will select 50 RRMS and 50 progressive MS (25 PPMS and 25 SPMS).

Figure 1.

1. MS diagnostic classifier

50 MS, 50 non-MS

non-MS diagnoses: ~25 NIND & ~25 OIND with high diagnostic certainty (CIS/RIS must be excluded, unless they progressed to definite MS)

2. RRMS vs PMS classifier

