50 RRMS, 50 PMS

PMS: ~25 PPMS & ~25 SPMS Minimum 3 years from untreated LP Can overlap w Cohort 1 &2

The cohorts of MS patients in 1-3 can overlap.

Select n=100-130 eligible MS patients

Required: ≥ 50 RRMS, ≥ 25 PPMS, ≥ 25 SPMS

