2. SELECTION AND ENROLLMENT OF SUBJECTS

2.1 Eligibility criteria

MS Patients selection criteria (n=100; Table 1)

- Lumbar puncture (LP) in the untreated stage with cryopreserved CSF (serum/blood optional) with consent to use it for future research
- \geq 3 years of follow-up from LP (with respect to the date of the scheduled follow up study visit)
- At time of LP untreated and not treated with steroid or off steroids ≥ one month
- Available/willing to come for in-person follow-up
- Available/willing to sign the NIH 09-I-0032 "Sample processing only" consent form
- Diagnosis of MS based on 2017 McDonald criteria at time of follow-up visit

Non-MS Patients selection criteria (n=50)

Required: 25 NIND, 25 OIND

- Lumbar puncture (LP) in the untreated stage with cryopreserved CSF (serum/blood optional) with consent to use it for future research
- \geq 3 years of follow-up from LP
- At time of LP untreated and not treated with steroid or off steroids ≥ one month
- Up to date contact information
- Available/willing to sign the NIH 09-I-0032 "Sample processing only" consent form
- Diagnosis:

NIND: e.g., ischemic-gliotic changes, CADASIL and other leukodystrophies, migraines, ischemic spinal cord lesions etc

OIND: e.g. CNS Sjogren's, SLE, vasculitis, CNS infections, MOG-associated disorders, NMO spectrum disorders (NMOSD)

Data and procedure at follow-up visit for MS patients:

- Signed consent for the present study and procedures.
 - Will include acknowledgment of NIH sample processing consent.
- Collection of a blood sample: one serum tube, four sodium heparin tubes and two potassium EDTA tubes [or one PAXGene tube] (see Figure 2 at the end of the protocol).
- Vital signs, weight, height and BMI.
- Complete neurological examination documented in NeurEx (recorded with an iPAD).
- Complete clinical data questionnaire with the patient.
- 25FW & non-dominant hand 9HPT (required for calculating CombiWISE & MS-DSS).
- Smartphone Apps (include 25FW, SDMT and tests that correlate highly w 9HPT can be acquired in patient-autonomous manner with minimal assistance).
- Optical Coherence Tomography (OCT).
- Propose optional LP to be done at the NIH.

Data and procedure at phone interview visit for MS patients:

- Phone interview consent for the present study and procedures.
 - Will include acknowledgment of NIH sample processing consent.
- Complete clinical data questionnaire with the patient.
- Propose optional LP to be done at the NIH.

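### The three budgeted centres fill diagnostic quotas from banked samples with known later course and no sampling order, so test 1 performance may be overstated for real practice

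*Combined protocol and SAP*

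**What the plan says.** The Synopsis gives the purpose: because the tests were developed at one research centre, "it is imperative to determine their performance in real clinical practice settings", as a step towards possible regulatory approval.

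Inclusion is described as selection to quotas:
- Section 1, item 1 (test 1, MS versus other disease): "we will select 50 patients with definite MS (CIS/RIS excluded) and 50 controls".
- Section 1, item 2 (test 2, relapsing-remitting versus progressive MS): "we will select CSF from 50 RRMS and 50 progressive MS patients (25 SPMS and 25 PPMS").
- Figure 1, overall pool: "Select n=100-130 eligible MS patients".
- Figure 1, test 1 controls: "25 NIND & ~25 OIND with high diagnostic certainty".

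Section 2.1 requires, for MS and non-MS patients alike, "Lumbar puncture (LP) in the untreated stage with cryopreserved CSF (serum/blood optional) with consent to use it for future research", together with at least 3 years of follow-up from that LP. For controls it gives example diagnoses and does not repeat or define the certainty rule. Table 1 in Section 2.3 divides the quotas among three budgeted centres. NIAID/NDS has no quota and gives every available patient who is non-overlapping and unpublished.

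Some provisions pull the other way. Figure 1 adds that "CIS/RIS must be excluded, unless they progressed to definite MS", so converters may enter, although Section 1, item 1 does not repeat the exception. Section 2.1 bases the MS diagnosis on the 2017 McDonald criteria at the follow-up visit. The NIND controls are "25 non-inflammatory neurological diseases (NIND) that mimic MS".

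**The concern.** A centre choosing from its bank already holds most of each patient's later history. With a quota to fill and no order of approach, it may skip an eligible patient whose picture was unclear at LP. Those are the patients for whom a diagnostic test would be ordered.

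Two kinds of certainty need to be kept apart. Certainty at follow-up is needed for a sound reference standard. Clarity at LP is not, and selecting on it produces spectrum bias: the easy cases and easy controls are over-represented, and AUROC, sensitivity and specificity move upward. A larger sample does not remove this bias and a confidence interval does not show it. Without a record of eligible patients left out, it cannot be checked afterwards.

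**Working it through.** **1. The plan's own figures.** Table 1 gives MS 60 + 20 + 20 = 100 (RRMS 30 + 10 + 10 = 50, PMS 50) and non-MS 30 + 10 + 10 = 50 (NIND 15 + 5 + 5 = 25, OIND 25). These match the quotas in Section 1. The three budgeted centres thus account for all planned patients, and the take-all rule at NIAID/NDS covers none of the quota. No target AUROC, precision or power is stated, so there is no sample-size figure to reproduce.

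**2. Which rules govern entry.**

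| Provision | Governs who enters? |
|---|---|
| Blinded assay and predefined models (Synopsis, Sections 1 and 2.4) | No, only measurement and scoring |
| MS by 2017 McDonald criteria at follow-up (2.1) | Sets the reference standard, not the order of choice |
| Mimic controls, CIS/RIS converters (Section 1, Figure 1) | Widens who may enter, does not require it |
| All available patients (2.3) | Yes, but at NIAID/NDS only |
| High certainty (Figure 1) | Yes, test 1 controls only, timing not stated |

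**3. Sampling error for scale.** Hanley-McNeil with A = 0.90 and 50 versus 50:
- Q1 = A/(2 − A) = 0.8182; Q2 = 2A²/(1 + A) = 0.8526.
- SE² = [0.09 + 49(0.8182 − 0.81) + 49(0.8526 − 0.81)]/2500 = 0.00103, so SE = 0.032.
- The same formula at A = 0.98 gives SE = 0.014.

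**4. Illustrative size.** All inputs here are assumptions. Scores are equal-variance binormal with d = √2·Φ⁻¹(AUROC), so d = 1.812 at 0.90. Each patient has a standard normal clarity C at LP. Within a group, C has correlation ρ with the score in the correct direction. The least clear share m is passed over, so C > Φ⁻¹(m). Then:
- both groups trimmed: AUROC = E[Φ((d + ρ(C₁ + C₀))/√(2(1 − ρ²)))];
- controls only: AUROC = E[Φ((d + ρC₀)/√(2 − ρ²))].

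From a true AUROC of 0.90, with ρ from 0.3 to 0.5:

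| Trimmed | m = 10% | m = 20% | m = 30% |
|---|---|---|---|
| Both groups | 0.917-0.930 | 0.928-0.948 | 0.937-0.961 |
| Controls only | 0.909-0.916 | 0.915-0.926 | 0.920-0.934 |

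The smallest shift is 0.009/0.032 = 0.3 SE and the largest is 0.061/0.032 = 1.9 SE.

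The result is sensitive to the inputs. With ρ = 0.1 and both groups trimmed, 0.90 becomes 0.905-0.912, a shift of at most 0.012 (under 0.4 SE). From a true 0.98, the development figure for test 1, trimming both groups at ρ = 0.3 to 0.5 gives 0.985-0.995, a shift of at most 0.015.

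**5. Cross-check with another model.** Suppose clear-cut patients alone have AUROC 0.98, and 20% of each group are ambiguous, with score means keeping only 0 to 0.5 of their distance from the midpoint. Including them gives AUROC 0.918-0.961. Sensitivity and specificity at the midpoint cut fall from 0.927 to 0.841-0.895. The direction is the same. The size differs because 0.98 is here the clear-case value and not the true one.

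**The case against.** A reader might infer that centres hand-pick easy cases and that performance will be overstated for both tests. The documents do not support that.

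- Selection is among patients who meet fixed criteria, and no section tells a centre to choose on clarity at LP. The text permits such choice and does not show it.
- NIAID/NDS takes all available patients, so the inference fails outright for that site.
- The natural reading of the certainty rule is certainty after follow-up. MS is explicitly judged then, controls need at least 3 years from LP, and Section 2 has the record checked to confirm the control diagnosis.
- CIS/RIS converters, by definition incomplete at first, may enter. Controls include MS mimics and other inflammatory disease, not healthy people.
- The certainty limit covers test 1 controls only. No such limit applies to relapsing-remitting versus progressive MS.
- The correlation and the share passed over have no source in the documents. A shift of 2 SE is not reached at an AUROC of 0.90.
- Eligibility is narrow and some strata are uncommon. Where a centre has few eligible patients, there is little room to choose. Pool sizes are not given.

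All of this stands, and it reduces the claim to a possibility centred on test 1. It does not supply a sampling order or a log at the three centres that fill the quotas, and it leaves the timing of control certainty to inference.

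**Conclusion.** The concern holds as a permitted bias and not a demonstrated one. The three budgeted centres may prefer clear-cut patients, and AUROC, sensitivity and specificity may then be too high for the setting that the Synopsis names. The case is strongest for test 1. For test 2 it rests only on subtype quotas without a sampling rule.

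The size cannot be derived from the documents. Under the assumptions in step 4 it ranges from negligible to nearly 2 SE at a true AUROC of 0.90. It is small in absolute terms if clarity and score are weakly related or if the true AUROC is near 0.98. The change is worth making because it is cheap and makes the real-practice claim checkable.

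**What to change.** In Section 1, Figure 1 and Section 2.3:

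1. Have each budgeted centre list all banked LPs that meet Section 2.1. It then approaches patients in order of LP date within RRMS, PPMS, SPMS, NIND and OIND until its Table 1 quota is filled. Where a stratum is small, it takes every eligible patient.
2. State that high diagnostic certainty for controls is judged at the follow-up of at least 3 years, as MS already is, and that an unclear picture at LP is not a reason to skip a patient.
3. Keep a log of eligible patients not included (reason, age, sex, LP date, diagnosis) and report how they compare with those included.

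The cost is protocol wording, one list per biobank and a simple log. The downsides are more approaches per enrolled patient and possibly a less favourable AUROC.

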50 RRMS, 50 PMS

PMS: ~25 PPMS & ~25 SPMS Can overlap w Cohort 1 &3

3. MS severity model

50 RRMS, 50 PMS

PMS: ~25 PPMS & ~25 SPMS Minimum 3 years from untreated LP Can overlap w Cohort 1 &2

The cohorts of MS patients in 1-3 can overlap.

Select n=100-130 eligible MS patients

Required: ≥ 50 RRMS, ≥ 25 PPMS, ≥ 25 SPMS

2. SELECTION AND ENROLLMENT OF SUBJECTS

2.1 Eligibility criteria

MS Patients selection criteria (n=100; Table 1)

- Lumbar puncture (LP) in the untreated stage with cryopreserved CSF (serum/blood optional) with consent to use it for future research
- \geq 3 years of follow-up from LP (with respect to the date of the scheduled follow up study visit)
- At time of LP untreated and not treated with steroid or off steroids ≥ one month
- Available/willing to come for in-person follow-up
- Available/willing to sign the NIH 09-I-0032 "Sample processing only" consent form
- Diagnosis of MS based on 2017 McDonald criteria at time of follow-up visit

Non-MS Patients selection criteria (n=50)

Required: 25 NIND, 25 OIND

- Lumbar puncture (LP) in the untreated stage with cryopreserved CSF (serum/blood optional) with consent to use it for future research
- \geq 3 years of follow-up from LP
- At time of LP untreated and not treated with steroid or off steroids ≥ one month
- Up to date contact information
- Available/willing to sign the NIH 09-I-0032 "Sample processing only" consent form
- Diagnosis:

NIND: e.g., ischemic-gliotic changes, CADASIL and other leukodystrophies, migraines, ischemic spinal cord lesions etc

OIND: e.g. CNS Sjogren's, SLE, vasculitis, CNS infections, MOG-associated disorders, NMO spectrum disorders (NMOSD)

Data and procedure at follow-up visit for MS patients:

- Signed consent for the present study and procedures.
 - Will include acknowledgment of NIH sample processing consent.
- Collection of a blood sample: one serum tube, four sodium heparin tubes and two potassium EDTA tubes [or one PAXGene tube] (see Figure 2 at the end of the protocol).
- Vital signs, weight, height and BMI.
- Complete neurological examination documented in NeurEx (recorded with an iPAD).
- Complete clinical data questionnaire with the patient.
- 25FW & non-dominant hand 9HPT (required for calculating CombiWISE & MS-DSS).
- Smartphone Apps (include 25FW, SDMT and tests that correlate highly w 9HPT can be acquired in patient-autonomous manner with minimal assistance).
- Optical Coherence Tomography (OCT).
- Propose optional LP to be done at the NIH.

Data and procedure at phone interview visit for MS patients:

- Phone interview consent for the present study and procedures.
 - Will include acknowledgment of NIH sample processing consent.
- Complete clinical data questionnaire with the patient.
- Propose optional LP to be done at the NIH.

Additional data to be collected after consent is obtained:

MS Patient data collected after follow-up or phone interview visit

Access electronic medical record (EMR) to collect/confirm the following information:

- Transcribing documented neurological examination completed within 1 month of the time of LP to EDSS or NeurEx.
- Detailed DMT history (with estimated date of initiation and termination of all drugs).
- Documentation of proximity of clinical relapse or contrast enhancing lesions (CELs) to the initial I P
- Estimation of subsequent relapse rate; conversion to clinically-definite MS (for original RIS/CIS) and possibly SPMS (for original RRMS).
- Imaging Data
 - If available, Brain MRI \pm 3 month of the **LP date:**
 - If images available transfer de-identified MRI images
 - If images are not available collect the following information:
 - 1) CEL if MRI done within a month from LP
 - 2) T2 lesion load (for MRI done within 3 months from LP)
 - 3) T1 black holes
 - If available, spinal cord MRI \pm 3 months of LP date:
 - If images available transfer de-identified MRI images
 - If images are not available collect the following information:
 - 1) CEL if MRI done within a month from LP
 - 2) T2 lesion load (for MRI done within 3 months from LP)
 - If available, Brain MRI (within 1 year of follow-up visit):

- If images available transfer de-identified MRI images
- If images are not available collect the following information:
 - 1) CEL if MRI done within a month from the follow-up visit
 - 2) T2 lesion load
 - 3) T1 black holes
- Spinal cord MRI around the time of follow-up visit:
 - If images available transfer de-identified MRI images
 - If images are not available collect the following information:
 - 1) CEL if MRI done within a month from follow-up visit
 - 2) T2 lesion load
- Available information for calculating BREMSO score (i.e., symptom onset: sphincter, motor, sensory; number of neurological functional systems involved at onset; incomplete recovery at onset).
- If available, 25FW/9HPT around the time of initial LP.

MS Patient data collected under consent waiver

Access electronic medical record (EMR) to collect/confirm the following information:

- Transcribing documented neurological examination completed within 1 month of the time of LP to EDSS or NeurEx.
- Transcribing documented most recently completed neurological examination available in medical record to EDSS or NeurEx.
- Detailed DMT history (with estimated date of initiation and termination of all drugs).
- Documentation of proximity of clinical relapse or contrast enhancing lesions (CELs) to the initial LP
- Estimation of subsequent relapse rate; conversion to clinically-definite MS (for original RIS/CIS) and possibly SPMS (for original RRMS).
- Available information for calculating BREMSO score (i.e., symptom onset: sphincter, motor, sensory; number of neurological functional systems involved at onset; incomplete recovery at onset).
- If available, 25FW/9HPT around the time of initial LP.

Non-MS Patient data collected after follow-up visit:

- Access electronic medical record (EMR) to confirm the clinical diagnosis.
- Contact the patient on the phone to confirm their availability to be contacted by the NIH to sign their consent.

2.3 Targeted patient number for each SPINCOMS center.

Table 1.

	MS patients	Non-MS patients	
	All require in-person follow-up visit	Do not require in-person follow-up but require data collection	
Wash. U	60 (30 RRMS, 30PMS)	30 (~15 NIND, ~15 OIND)	
U. Ottawa	20 (10 RRMS, 10PMS)	10 (~5 NIND, ~5 OIND)	
U. Colorado	20 (10 RRMS, 10PMS)	10 (~5 NIND, ~5 OIND)	
NIAID/NDS	None budgeted, but will contribute all available that are non-overlapping and unpublished	None budgeted, but will contribute all available that are non-overlapping and unpublished	

^{*}University of Montana will not participate in patient recruitment, data analysis only

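### The centre that developed the tests may add an unstated number of its own new patients to a validation meant to be independent, and no primary validation set is named

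*Combined protocol and SAP*

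**What the plan says.** The Synopsis gives the reason for the study: "Because these results are derived from a single research center (NIAID/NDS), it is imperative to determine their performance in real clinical practice settings". Aim 1 promises an independent validation, in 100 new patients per test, within the multicentre SPINCOMS consortium.

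Table 1 (section 2.3) sets recruitment targets for Washington University, Ottawa and Colorado. For NIAID/NDS, the MS and the non-MS cells carry the same entry: "None budgeted, but will contribute all available that are non-overlapping and unpublished". No number, cap or share follows.

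Section 1, item 1, fixes the diagnostic comparison: "we will select 50 patients with definite MS (CIS/RIS excluded) and 50 controls". Figure 1 gives a wider pool for the MS cohorts: "Select n=100-130 eligible MS patients". It does not tie that range to any centre, and there is no matching range for non-MS patients.

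The one statement on accuracy analysis is in section 1, item 3, and covers the two classifiers: "Results will then be unblinded and analyzed for accuracy of diagnostic conclusion". It says nothing about centre. The contents page lists a section 9.5 on data analyses, but the numbered body runs from 1 to 5 and contains no such section. Section 2.4 does provide for a Site ID in the clinical data.

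**The concern.** The question Aim 1 has to answer is how the tests perform away from the centre that built them. Patients from that centre, even new ones, may share its referral mix, CSF handling and raters with the development sample. If they enter the validation sample and one overall AUROC is reported, the reader cannot tell how much of it is external performance.

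The plan does not say these patients will be pooled. It does not say they will be excluded or analysed apart either, so the choice could be made after unblinding. They could enter by two routes, and no rule governs either: selection into a cohort drawn from 100 to 130 MS patients, or replacement of patients whom the other centres fail to recruit.

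**Working it through.** **1. The plan's own totals (Table 1 against section 2.1).**
- MS: 60 + 20 + 20 = 100, made up of 30 + 10 + 10 = 50 RRMS and 50 PMS. Section 2.1 states 100.
- Non-MS: 30 + 10 + 10 = 50, made up of 15 + 5 + 5 = 25 NIND and 25 OIND. Section 2.1 states 50.

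The three other centres therefore fill every planned comparison with no NIAID/NDS patients.

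**2. A possible share.** The documents give none. *Assumption:* NIAID/NDS supplies the 30 places between 100 and 130 MS patients, which is 30/130 = 23%. A proportional draw of 50 MS patients then holds 50 × 30/130 = 11.5, taken as 12.

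**3. Pooled AUROC, diagnostic test, targets met.** *Assumptions:* all controls are external; NIAID/NDS keeps its development AUROC of 0.98; scores are normal with unit variance and centred alike across centres. Each centre's case and control means are then ±√2·Φ⁻¹(AUROC)/2, and each case-source by control-source pair contributes Φ((μ_case − μ_control)/√2), weighted by its share of pairs.

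At external 0.85 the external means are ±0.733 and the NIAID/NDS case mean is 1.452. NIAID/NDS cases against external controls give Φ((1.452 + 0.733)/√2) = 0.939. Pooled: 0.76 × 0.85 + 0.24 × 0.939 = 0.871.

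| True external AUROC | 0.75 | 0.80 | 0.85 | 0.90 | 0.95 |
|---|---|---|---|---|---|
| Pooled AUROC | 0.789 | 0.830 | 0.871 | 0.913 | 0.954 |

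**4. Against sampling error.** Hanley-McNeil: SE² = [A(1−A) + (n₁−1)(Q₁−A²) + (n₀−1)(Q₂−A²)]/(n₁n₀), with Q₁ = A/(2−A) and Q₂ = 2A²/(1+A). At A = 0.85 with 50 v 50, SE = 0.0391 and the 95% half-width is 1.96 × 0.0391 = 0.077. The shift is 0.871 − 0.850 = 0.021.

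Coverage of the true external 0.85 by the nominal 95% interval (40,000 simulated 50 v 50 datasets per case):

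| Sample | Coverage |
|---|---|
| External patients only | 94% |
| 12 NIAID/NDS MS, that centre at 0.98 | 87% |
| 12 NIAID/NDS MS, that centre at 0.95 | 90% |
| 12 NIAID/NDS MS, that centre at 0.90 | 93% |

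The pooled AUROCs in the last two rows are 0.864 and 0.856. With the centre at 0.98, about 13% of intervals lie wholly above the external value, against about 5% with external patients only.

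**5. Sensitivity to a centre-level score shift (external 0.85, NIAID/NDS at 0.98).**
- NIAID/NDS MS scores 0.5 SD lower: 0.858.
- 0.72 SD lower: no shift.
- 1 SD lower: 0.838, so the direction reverses.
- 1 SD higher: 0.883.

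At external 0.95 the direction reverses beyond about 0.3 SD lower.

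**6. Shortfall case.** *Assumption:* 10 of the 50 controls and 10 of the 50 MS patients come from NIAID/NDS. Pooled: 0.2² × 0.98 + 0.8² × 0.85 + 2 × 0.2 × 0.8 × 0.939 = 0.884. Coverage falls to about 79%. The direction reverses only if all NIAID/NDS scores move by more than about 1.56 SD either way.

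**7. RRMS v PMS classifier.** *Assumptions:* the same 30 places are split evenly, giving 12 + 12 of 50 v 50, and NIAID/NDS stays at its development 0.91. External 0.85 pools to 0.24² × 0.91 + 0.76² × 0.85 + 2 × 0.24 × 0.76 × 0.883 = 0.865. External 0.80 pools to 0.829.

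**8. Severity test.** Not computed: the documents give no means or variances by site.

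**The case against.** The case against is substantial. This is a silence and not a misstatement: nothing says the patients will be pooled, and harm needs both pooling and a real difference between centres. The natural reading, with none budgeted and the other centres filling the totals exactly, is that NIAID/NDS is a supplement. Aim 1 speaks of validation within SPINCOMS, and section 2.3 lists NIAID/NDS as a SPINCOMS centre. If consortium-wide performance is the target, including its patients is not bias, and the coverage figures measure a quantity the plan never names. New patients only, pre-defined models, blinded assay and a recorded Site ID all limit the damage. The figures stack assumptions, the sign can reverse, and the main-case shift is below sampling error. At external 0.95 coverage drops only from about 94.5% to 92%.

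All of that stands as a limit on size. It does not settle which patients carry the claim of independence. The Synopsis gives the single-centre origin as the reason for the study, and the safeguards prevent patient re-use and unblinded assessment, not shared centre characteristics. A Site ID makes a split possible but does not commit anyone to making it before the results are known.

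**Conclusion.** The concern holds and should be fixed. The plan admits an unstated number of patients from the development centre and leaves the primary validation set open, on the very question the study was set up to answer.

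The numerical effect is conditional. With targets met, it is modest: about 0.00 to 0.04 on the AUROC scale for the diagnostic test over external values of 0.95 to 0.75. It is upward when scores are aligned across centres and reversible when they are not. The assumed shortfall case is larger, at 0.034 with coverage near 79%. There is no effect if new patients perform and score alike at all centres. The shares, the external AUROCs and the score model are assumptions; only the centre totals and the development values of 0.98 and 0.91 come from the documents. Confidence is medium for that reason.

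**What to change.** Before unblinding, add a short statement to section 2.3 and beside the accuracy sentence in section 1 (or in section 9.5, if the section listed in the contents is written):

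- The primary validation analysis of each of the three tests uses only Washington University, Ottawa and Colorado patients.
- NIAID/NDS patients, identified by Site ID, are reported as a separate same-centre set and in a pooled secondary analysis.
- If NIAID/NDS patients fill a shortfall, that analysis is labelled as such and the result without them is shown beside it.

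Enrolment does not change, and NIAID/NDS patients stay available for Aim 2. If the three centres meet target, no precision is lost against the planned 50 v 50. If they fall short, the primary interval widens modestly: at AUROC 0.85 the 95% half-width goes from 0.077 (50 v 50) to 0.079 (50 MS v 40 controls) or 0.086 (40 v 40).
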